However, what this abnormal connectivity in MSABI is caused by is not established. Multiple contributors to the abnormal connectivity in MSABI are possible. In addition to seizures, others include increased intracranial pressure from edema, hemorrhage, or hydrocephalus, or alternatively, cortical spreading depolarizations^{15,16}. **If the abnormal network patterns in MSABI correspond to those seen in seizure networks of epilepsy and are modulated by antiseizure medication, then there may be a relationship with epileptogenic brain activity.** While this is not definitive proof of epileptogenic causation or change in outcome, instead ASM delivery in those with MSABI and seizure networks is an initial logical perturbation of this complex network system to determine if further investigation is warranted.

[figure not shown]

Table 2. Treated SzNET

Treatment: 5 of 6 patients with phenobarbital load 20 mg/kg x 3 days and 1 patient with levetiracetam load 60 mg/kg	
EEG-	60%
DoC improvement*	100%
SzNet improvement	100%
EEG improvement in those EEG+	100%

*DoC improvement defined by care teams' documentation of patient exam improving by one level of DoC within 14 days of therapy. Example from coma to unresponsive wakefulness syndrome (UWS), or from UWS to minimal responsiveness syndrome (MCS).

improvement.

In our preliminary retrospective SABI data in adults and children (N=63), 30% were EEG- and SzNET+ (Fig. 1). Regarding initial evidence of SzNET response to ASM in SABI, of the 63 SABI patients who received rs-fMRI, 27 (42%) had SzNet; of these, 6 received ASM therapy driven by clinician interpretation of rs-fMRI results described in Table 2 with network and outcome

In epilepsy, SzNET also disrupt the RSN, impacting the patient phenotype, such as memory capacity reduction^{17,18}. Since Resting State Networks (RSN) connectivity is associated with consciousness recovery in DoC^{19,20}, then **SzNET may also be disrupting RSN connectivity in MSABI, producing prolonged DoC.** In our case series SABI- SzNET treatment experience described in Table 1, the RSN connectivity also improved with therapy. Thus, it is also possible that by tracking not only the therapy impact on SzNET but also the RSNs, especially the default mode network, that is highly associated with SABI DoC recovery^{21,22}, we may better understand the link of SzNET disruption of RSN and possible mechanism of prolonged DoC in SABI.

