4.3. Measurement Design

Table 2. Variables of interest: their occasions of evaluation, their uses for the aims, their roles in the study

Variables within Domains	Scale ¹	Occasions ²	Aims ³	Main Roles
Identifiers				
Participant's unique ID	nominal	all	all	identifier

Intervention	categorical	E	All, except aim 2	intervention
Clinical Health Profile				
Spontaneous ventilation	Binary	E, 2	Aim 1	Exploratory uses
Glasgow Coma Scale (GCS)	Ordinal 3-15	S, E, 2	--	Screening
weight	kg	E	--	dosing
height	cm	E	--	dosing
body mass index (BMI)	kg/cm ²	E	--	dosing
body surface area (BSA)	kg/m ²	E	--	dosing
Supratentorial decompressive craniectomy	Binary	S, E, 2	--	Exploratory uses
age	decimal yrs	S	--	screening
sex	categorical	S	--	Exploratory uses
Pre-MSABI BIS (appendix a)	Ordinal 0-100	S	--	screening
Medical Records				
Presumed etiologies of disorder of consciousness	Categorical	S	--	screening
co-morbidities list	nominal	S	--	screening
Clinical tests				
2HELP2B Score	Ordinal 0-7	S	--	Exploratory uses
pre-intervention EEG status (EEG monitoring Seizures)	Binary	E	All	classification
Research tests				
SzNET presence	Binary	E	All	Classification and primary outcome
Total Volume (TV)	continuous	2	Aim 1a	primary outcome
Total Volume Reduction (TVR)	continuous	2	Aim 1a, 3, 4	primary outcome
Power Spectrum (PS)	continuous	2	Aim 1b	primary outcome
Power Spectrum Improvement (PSI)	continuous	2	Aim 1a, 3, 4	primary outcome
Typical RSN improvement	Binary	2	Aim 4	Secondary outcome
EEG improvement	Binary	2	Aim 3	Secondary outcome
Protocol Time Frames				
Days of antiseizure medication	Days (discrete)	2	-	Confounder
Time from MSABI to rs-fMRI#1 (days)	Days (discrete)	2	-	Confounder
Time from MSABI to rs-fMRI#2 (days)	Days (discrete)	2	-	Confounder
Time from MSABI to treatment protocol start (days)	Days (discrete)	2	-	Confounder
Time from enrollment to rs-fMRI#1	Days (discrete)	2	-	Secondary outcome
Questionnaires/survey instruments⁴				
Anxiety: PROMIS Emotional Distress—Anxiety—Short Form (appendix H)	Ordinal 7-35	3	Aim 5	Exploratory outcome

Depression: Neurological Disorders Depression Inventory for Epilepsy (NNDI-E) (appendix I)	Ordinal 6-24	3	Aim 5	Exploratory outcome
Quality of Life: QOLIE-10-P (appendix J)	Ordinal 1-10	3	Aim 5	Exploratory outcome
Telephonic Montreal Cognitive Assessment (appendix K)	Ordinal 0-15	3	Aim 5	Exploratory outcome
ASM toxicity: Liverpool adverse event profile test (appendix L)	Ordinal 19-76	3	Aim 5	Exploratory outcome

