Investigate association between post-intervention EEG improvement and SzNET response. The outcome of interest is the relative risk of EEG improvement in patients with more than 50% improvement of their SzNET by TVR and PSI.

H_0 : there will be no difference in the EEG improvement between the patients with and without more than 50% improvement of their SzNET.

H_1 : EEG improvement will be greater in the patients with more than 50% of SzNET improvement.

There are 22 subjects used in Aim 3. We will fit logistic regression model to characterize the association between the EEG improvement with the patients with and without more than 50% improvement of either PSI or TVR. We will use the Wald test and likelihood ratio test statistics to test the null and alternative hypotheses.

Plans for Aim 4.

Investigate association between the post-intervention typical resting state networks (RSN) connectivity improvement and the SzNET response. The outcome of interest is the relative risk of improvement of the typical RSN in the patients with more than 50% of improvement of their SzNET by TVR and PSI.

H_0 : there will be no difference in the typical resting state networks connectivity improvement between the patient with and without more than 50% improvement of their SzNET.

H_1 : Median typical resting state networks connectivity improvement will be greater in the patients with more than 50% of SzNET improvement.

There are 22 subjects used in Aim 4. We will fit logistic regression model to correlate the RSN improvement with the patients with and without more than 50% improvement of either PSI or TVR and use the Wald test and likelihood ratio statistics to test the null and alternative hypotheses.

Plans for Aim 5.

Describe psychosocial functional measure outcomes and ambulatory ASM toxicity at 3 months from discharge. The outcomes of interest will be the PROMIS Emotional Distress—Anxiety— Short Form, the Neurological Disorders Depression Inventory for Epilepsy (NNDI-E), the QOLIE-10-P, the Telephonic Montreal Cognitive Assessment, and the Liverpool adverse event profile test. All will be assessed at the 3 month follow-up visit to one of the NSICU Post-Discharge clinics.

Plans for Aim 6.

Aim 6 is to assess the trial's design feasibility success in enrollment and retention by evaluating the enrollment rate and dropout rate among participants at the end of the trial.

Aim 6a

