8.4. Planned Interim Analyses

No interim analyses will be performed.

9. Sample Size Rationale

There is no preliminary data for effect size estimation using the paradigm and patient population suggested in this study. In Aim 1, a paired t-test is used to test measurement differences before and after ASM. A effect size 0.806 can be detected for a 1-sided test at a power of 80% and a Type I error at 0.05 with the total of 11 subjects before and after ASM. In Aim 4, a transformed Z-test is used to test correlation between two variables. A correlation size 0.506 can be detected for a 1-sided test at a power of 80% and a Type I error at 0.05 with the total of 22 subjects.

10. Data Capture and Database Management

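### Aims 3 and 4 cut continuous TVR and PSI at 50% before testing, which loses power in about 20 patients and, if most respond, leaves a small comparison group with frequent empty cells

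*Combined protocol and SAP*

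**What the plan says.** The variables table in Section 4.3 gives TVR and PSI a continuous scale and assigns both to Aims 3 and 4. The text below it defines clear SzNET improvement as a value above 0.5 on TVR or PSI.

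Section 8.3 uses only that indicator. For Aim 3 the logistic model describes "the association between the EEG improvement with the patients with and without more than 50% improvement of either PSI or TVR". For Aim 4 it is fitted to "correlate the RSN improvement with the patients with and without more than 50% improvement of either PSI or TVR". Both outcomes (EEG improvement, RSN improvement) are binary, and both aims are tested by Wald and likelihood ratio statistics. Neither names an exact or penalised fallback or an analysis of TVR or PSI as measured. Sections 3.3 and 3.4 state the target as a relative risk at the 50% cut and join TVR and PSI by "and", whereas the models use "either ... or".

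On numbers, Section 8.3 says "There are 22 subjects used in Aim 3" and "There are 22 subjects used in Aim 4". Section 5.1 expects 20 of 22 treated patients to complete, and Section 7.8 limits dropouts' data to Aim 2.

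Section 9 sizes Aim 4 on a different test: "a transformed Z-test is used to test correlation between two variables", and "A correlation size 0.506 can be detected for a 1-sided test at a power of 80% and a Type I error at 0.05" with 22 subjects. Aim 3 has no power statement.

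**The concern.** A yes/no at 0.5 treats a TVR of 0.49 as no response and one of 0.51 as full response, and ignores all other differences between patients. With about 20 patients there is little information to spare. If many patients respond, the comparison row of the 2x2 table is short, an empty cell becomes likely, and the maximum-likelihood odds ratio and its Wald test break down.

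At stake is whether EEG or RSN improvement follows SzNET response. Section 4.2 names the correlation with EEG response as one of two important aspects of the biomarker to be explored for the larger trial. The cut also sits oddly with the protocol's own reasoning. Section 4 accepts alternative regimens partly because the main outcomes are quantitative and could show smaller effects, and Section 4.3 defends the wide age range partly by the quantitative treatment of SzNET. The change log explains the move to logistic regression by the binary outcomes. No reason is given for cutting the predictor.

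**Working it through.** **1. The plan's figure.** Fisher z, n = 22, one-sided 0.05, r = 0.506: atanh(0.506) x sqrt(19) - 1.645 = 0.557 x 4.359 - 1.645 = 0.784, so power is 78%. With the small-sample bias term and a t-based critical value it is 80.0%. The stated figure reproduces, but for a correlation between two uncut variables. At n = 20 the same formula gives 74%.

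**2. The cut in the plan's own framework.** Cutting a normal predictor with a share p above the cut multiplies the correlation by phi(z_p)/sqrt(p(1-p)). At p = 0.5 this is 0.399/0.5 = 0.798, and 0.506 x 0.798 = 0.404.

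| Share above cut | Reduced r | Power, n = 22 | Power, n = 20 | n for 80% power |
|---|---|---|---|---|
| 50% | 0.404 | 59% | 55% | 37 |
| 70% | 0.384 | 55% | 51% | 41 |
| 80% | 0.354 | 49% | 45% | 49 |
| 90% | 0.296 | 38% | 35% | 70 |

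**3. The planned models, by simulation.** Inputs: n = 20 (Sections 5.1 and 7.8), one-sided 0.05 (Section 9) and, as assumptions, bivariate normal latent response and improvement with correlation 0.506 and half the patients improving. Section 9 does not describe 0.506 as a latent correlation, so it serves here only as a benchmark. The documents give no rate of passing 50%, so a range is shown. Expected non-responders are 20(1-p), and the chance of none is p^20 (0.8^20 = 0.012; 0.9^20 = 0.122).

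| Share above cut | LRT on cut | Wald on cut | Expected non-responders | P(none) | Empty cell |
|---|---|---|---|---|---|
| 50% | 47% | 39% | 10 | about 0 | - |
| 70% | 45% | 21% | 6 | 0.1% | 21% |
| 80% | 42% | 7% | 4 | 1.2% | 44% |
| 90% | 28% | 1% | 2 | 12% | 78% |

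With the predictor left continuous the share above 0.5 does not matter. Logistic regression with a likelihood ratio test has about 62-63% power, and the exact rank sum test 54-55%. Between the two likelihood ratio tests, the cut therefore costs about 15 points at an even split (62 - 47) and about 34 at 90% (62 - 28).

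**4. Test size.** With no association, the likelihood ratio test on the cut rejects in 5.7-6.9% of trials and the rank test in 4.5-4.8%. A check shows the continuous likelihood ratio test to be liberal to about the same degree as the cut version. The comparison between those two is fair, but part of their lead over the rank test is excess type I error. The penalised form was not simulated.

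**5. The pilot.** Six of six gives an exact two-sided 95% lower limit of 0.025^(1/6) = 54%.

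**The case against.** Five points can be made for the plan.

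- **The pilot.** A reader might infer from "SzNet improvement" in 100% of six treated patients (Section 2.1) that nearly everyone will pass 50% and no comparison group will remain. The documents do not support this. The table gives no size of improvement, clinicians chose who was treated, and the group is empty only if every patient passes the cut. Even if all six had passed it, the rate could be anywhere from about half upwards. This stands.
- **The outcome may be lopsided too.** The same table reports EEG improvement in all EEG+ patients. If 90% improve on the outcome, the rank test has about 31-32% power, against 28%, 33% and 28% for the likelihood ratio test on the cut when 50%, 70% and 90% exceed it. The rank test then lacks a comparison group in about 12% of trials. This stands, and is why the rank test should not be the main analysis.
- **Response may be two-class.** Section 4.1 expects the drugs to act selectively on networks of epileptogenic origin. With assumed class means of 0.8 and 0.2, the cut beats the rank test (for example 56% against 42% at 70% responders and SD 0.15). The continuous logistic likelihood ratio test trails the cut by about 3-8 points when the classes are sharply separated. This stands as a limit on the gain.
- **The cut is prespecified and part of the target.** This is true. A continuous test does not estimate the relative risk, so the relative risk has to be kept as a reported summary.
- **Section 8.1 already lists the Wilcoxon rank sum test among the primary tools.** That wording is generic and does not replace the specific Wald and likelihood ratio tests on the cut in Section 8.3. It does show that the remedy is within the planned methods.

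**Conclusion.** The concern holds as a loss of power and a risk of failed estimation. At a latent correlation of 0.506, with n = 20 and half improving, the cut lowers likelihood ratio power from about 62-63% to about 47%, 45% and 28% as the share above 50% rises from 50% to 70% to 90%. The Wald test, also planned, falls to about 1%. Empty cells, which leave no finite odds ratio and an unusable Wald test, occur in about 21%, 44% and 78% of trials at 70%, 80% and 90% responding.

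The response rate, outcome rate and smooth association are assumptions. A reader might also infer that a continuous analysis would settle Aims 3 and 4. It would not: no analysis considered reaches 80% power at 0.506, because the outcome is binary as well. These are secondary outcomes in a pilot, so this is a cheap improvement, not a fault that undermines the trial.

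**What to change.** In Section 8.3, for Aims 3 and 4:

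1. Make the test a logistic regression of EEG or RSN improvement on continuous TVR, and separately on PSI, with penalised likelihood. Use a likelihood ratio test and interval, not Wald, and report the odds ratio per 0.1 of TVR or PSI.
2. Add the exact rank sum comparison of TVR and PSI between improved and not improved patients as a sensitivity analysis.
3. Keep the relative risk at the 50% cut, with an exact confidence interval, as a descriptive summary. State one rule for passing the cut, since Sections 3.3 and 3.4 say "and" while Section 8.3 says "either ... or".
4. In Section 9, restate what Aims 3 and 4 can detect for the model that will be fitted and for about 20 patients.

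The cost is SAP wording plus one recalculation, with no extra data. The hypothesis test would no longer target the relative risk at 50% directly, and a little power may be lost if response is truly two-class. The change should be made before any Aim 3 or 4 data are analysed.

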Investigate association between post-intervention EEG improvement and SzNET response. The estimand of interest is the relative risk of EEG improvement in patients with more than 50% improvement of their SzNET by TVR and PSI.

3.4. Aim 4

Investigate the association between the post-intervention typical resting state networks (RSN) connectivity improvement and the SzNET response. The estimand of interest is the relative risk of improvement of the RSNs in the patients with more than 50% of improvement of their SzNET by TVR and PSI.

3.5. Aim 5

Describe psychosocial functional measure outcomes and ambulatory ASM toxicity at 3 months from hospital discharge. The estimates of interest will be the PROMIS Emotional Distress—Anxiety— Short Form, the Neurological Disorders Depression Inventory for Epilepsy (NNDI-E), the QOLIE-10-P, the Telephonic Montreal Cognitive Assessment, and the Liverpool adverse event profile test. All will be assessed at the 3 month follow up visit by one of the NSICU Post-Discharge clinics. This aim only applies to the patients that are discharged alive from the hospital and will include results from visits until 14 months after the enrollment start.

3.6. Aim 6

Assess the trial's design feasibility success in enrollment and retention for our actual institutional context by evaluating the enrollment rate and dropout rate among participants at the end of the trial. It will be composed by two sub aims.

Aim 6a

Measure the participants enrollment rate during the hole study enrolling months. The estimand of interest will be the rate of enrolled patients per month.

Aim 6b

Measure the participants dropout rate among participants. The estimand of interest will be the dropout rate from the total enrolled participants at the end of the study.

4. Study Design

This is a prospective interventional, uncontrolled, open-label, single center pilot study in moderate to severe acute brain injury (MSABI) patients with suppression of consciousness. The study main outcomes require pre and post-intervention rs-fMRI data collection to characterize the evolution of SzNET, a physiological measure of brain function. Clinical implementation of rs-fMRI is still novel, not frequently performed at early stages of MSABI, and has few medical indications as a follow-up test. As this data is infrequently generated during the standard of care (SOC), a prospective interventional study with an ASM intervention and a research funded rs-fMRIs is needed.

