It will be used to investigate the association in patients with a clear improvement of their SzNET. Such improvement will be defined as more than 0.5 TVR or 0.5 PSI threshold.

- RSN improvement is a binary variable collected by the study coordinator based on clinical records of the rs-fMRI#2, taking into consideration the spatial and temporal features and the number of canonical RSN

observed in the rs-fMRI#2. It will be used to investigate association in patients with a clear improvement of their SzNET; such improvement will be defined as more than 0.5 TVR or 0.5 PSI threshold.

- All the variables listed as exploratory will be studied for association in patients with clear improvement of their SzNET, such improvement will be defined as more than 0.5 TVR or 0.5 PSI threshold.

-

Comments regarding extended age range: 18 months to 70 years of age had heterogeneity of brain function related to both neurodevelopment and old-age related degenerative processes. However, the impact of seizure on brain networks that causes suppression of consciousness is similar through these age groups. For example when seizure occurs we expect reduction in consciousness in both young and old who have either epilepsy or acute brain injury. Patient's age may have impact on the clinical outcomes and connectivity aspects of resting state networks, for that reason we will analyze seizure networks (SzNET) different to the typical resting state networks (RSN). The analytical approach to SzNET that depend mostly on the ictal activity will be quantitative, but RSN improvement is a binary variable based on experts opinion judging the presence or absence of these normal networks that are described and used for neuroprognostication across different age groups³⁰⁻³²

Safety and Feasibility Variables:

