8.1. Strategies that Apply to all the Aims

All statistical procedures will be performed in SAS and R. Biostatistician [name] will oversee all data analyses.

- (i) All data will be scored and rescored by separate staff members and checked for accuracy prior to double entry into our database. All datasets are backed up daily.

- (ii) Prior to statistical modeling, we will perform descriptive analyses and data visualizations to examine the distributions of all measures. Appropriate transformations to obtain approximate normality will be performed; where necessary, additional nonparametric tests will confirm results.
- (iii) Linear regression model and nonparametric tests (e.g., Wilcoxon rank sum test) will be the primary analytic tools for testing our *a priori* hypotheses. Model selection methods (e.g., Bayesian information criterion) and sensitivity analysis methods will be used to select models and assess various model assumptions. We will consider the use of appropriate covariates as detailed below in all aims.
- (iv) We will record the reasons for drop-outs, missing / censored data values, and protocol departures in the database. We will appropriately handle drop-outs and missing data (e.g., missing responses and/or covariates) by using imputation or other estimation methods (e.g., missing completely at random), while considering anticipated causes. We will carry out sensitivity analysis to evaluate different missing mechanisms.
- (v) We will use test statistics (e.g., likelihood ratio test) to test the hypotheses. To identify significant component terms in each of the models, we will examine the parameter estimates, 95% confidence intervals, and p-values of the component terms in an analysis of fixed effects for the final regression models. All statistical estimates of population parameters will be tabulated along with corresponding confidence intervals (CIs) and/or standard errors (SEs) to convey levels of precision / imprecision.

We will use graphical methods such as forest plots to visualize the analysis results. We will also include outcome-dependent exploratory analyses to generate new hypotheses.

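### Aims 3 and 4 word the responder rule inconsistently, give no step from the logistic model to the relative risk, and name two tests without saying which decides

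*Combined protocol and SAP*

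**What the plan says.** **Responder rule.** Section 3.3 describes the Aim 3 group as patients with "more than 50% improvement of their SzNET by TVR and PSI". Section 3.4 gives the Aim 4 estimand as the "relative risk of improvement of the RSNs in the patients with more than 50% of improvement of their SzNET by TVR and PSI". Section 8.3 restates the Aim 3 outcome as the "relative risk of EEG improvement in patients with more than 50% improvement of their SzNET by TVR and PSI". Section 4.3, defining clear SzNET improvement, says: "Such improvement will be defined as more than 0.5 TVR or 0.5 PSI threshold". The Section 8.3 models follow 4.3. Aim 3 relates "the EEG improvement with the patients with and without more than 50% improvement of either PSI or TVR", and Aim 4 will "correlate the RSN improvement with the patients with and without more than 50% improvement of either PSI or TVR". The variables table in Section 4.3 lists TVR and PSI on separate rows, each assigned to both aims.

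**Effect and model.** The effect is a relative risk; the only model is logistic regression. Section 8.1(v) promises confidence intervals and/or standard errors for all estimates.

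**Tests.** For Aim 3: "We will use the Wald test and likelihood ratio test statistics to test the null and alternative hypotheses". Aim 4 has an equivalent sentence. Section 8.1(v) mentions one of the two only as an example: "We will use test statistics (e.g., likelihood ratio test) to test the hypotheses". The alternatives are directional, but Section 8.3 states no sidedness.

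**Related text.** The Aim 4 alternative hypothesis is about a median, although Section 4.3 makes RSN improvement binary. Section 9 sizes Aim 4 with a one-sided transformed Z-test of a correlation (0.506, 22 subjects, 80% power, 0.05). Section 8.3 counts 22 patients, while Section 5.1 expects 20 with a repeat scan.

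**The concern.** The responder flag is the only exposure in both aims, so its definition fixes the 2x2 table. A patient with TVR 0.6 and PSI 0.2 is a responder under *or* and a non-responder under *and*.

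Logistic regression reports an odds ratio, which lies well away from the relative risk when improvement is common. If the step between them is left open, the estimand may be reported on the wrong scale.

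The two named tests agree closely in large samples but not in sparse tables. With 20–22 patients, LR can be significant where the Wald test is not, or cannot be computed. The plan does not say which one is the result.

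Section 4.2 names the link between SzNET and EEG response as one of two aspects of the biomarker that the design explores. What is at stake is an ambiguous signal for the larger trial.

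**Working it through.** **1. The plan's own figure.** Section 9, Aim 4: n = 22, one-sided 0.05, power 80%. The plain Fisher z form gives tanh((1.645 + 0.842)/√19) = 0.516. Adding the bias term, atanh(r) + r/(2(n−1)) = 2.487/√19, gives 0.507. Using the t-based critical correlation as well gives 0.506, with power 0.7995 at that value. The figure reproduces, but for a correlation test that Section 8.3 does not use for two binary variables. At n = 20 the same test has power 0.74 to 0.76.

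**2. Responder rule.** The documents give no pass rates at the 50% threshold. Assume that a share p passes each threshold and that TVR and PSI are bivariate normal with correlation ρ. Patients classified differently by the joint and composite rules = 20 × (2p − 2P(both)).

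| p | ρ | *and* | *or* | differ |
|---|---|---|---|---|
| 0.5 | 0.3 | 6.0 | 14.0 | 8.1 |
| 0.7 | 0.5 | 11.1 | 16.9 | 5.7 |
| 0.8 | 0.9 | 15.0 | 17.0 | 2.0 |

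Over p = 0.5–0.8 and ρ = 0.3–0.9 the range is 2.0 to 8.1. The *or* rule leaves few non-responders, so splits such as 16 vs 4 or 17 vs 3 are realistic.

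**3. Effect measure.** 80% vs 40%: RR = 0.8/0.4 = 2; OR = (0.8/0.2)/(0.4/0.6) = 6. 90% vs 60%: RR = 1.5; OR = (0.9/0.1)/(0.6/0.4) = 6. The same odds ratio can stand for different relative risks.

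**4. The two tests.** For a of n1 responders and c of n2 non-responders improved:

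- LR: G = 2[ℓ(a,n1) + ℓ(c,n2) − ℓ(a+c, n1+n2)], with ℓ(k,n) = k ln(k/n) + (n−k) ln((n−k)/n), on 1 df.
- Wald: |log OR| / √(sum of reciprocal cell counts), which has no finite value when a cell is empty.

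Example, 17/17 vs 2/3: G = 2(0 − 1.910 + 3.970) = 4.12, p = 0.042. Wald has no finite estimate. Fisher p = 3/20 = 0.15.

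All binomial pairs at n = 20 were enumerated exactly, two-sided at 0.05, with an empty-cell Wald test counted as non-significant. The entries are the chance that LR is significant and Wald is not:

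| Split | 80 vs 40 | 60 vs 30 | 70 vs 50 | 80 vs 20 | 90 vs 20 | 95 vs 30 |
|---|---|---|---|---|---|---|
| 10 vs 10 | 17% | 6% | 6% | 22% | 43% | 64% |
| 16 vs 4 | 27% | 25% | 12% | 54% | 62% | 65% |
| 17 vs 3 | 31% | 28% | 15% | 60% | 70% | 68% |

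The reverse (Wald significant, LR not) never occurs here. For the three large contrasts, the part arising without an empty cell is 1–3 points at 10 vs 10 and 7–12 points at the unequal splits.

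**5. LR size, two-sided.** At a common improvement rate of 50% or 70%: 5.2% and 7.7% (10 vs 10); 10.2% and 7.6% (16 vs 4); 12.6% and 5.5% (17 vs 3).

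**The case against.** *By TVR and PSI* may only name the two measures, and *either PSI or TVR* may mean one model per measure. The variables table supports that reading. This stands: a reader might infer that *or* is plainly the rule and *and* a slip, but the documents do not settle it. The request is therefore for a statement, not for one particular rule.

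A reader might infer that no interval is planned for the relative risk. Section 8.1(v) promises intervals or standard errors for all estimates, and with one binary covariate the relative risk follows from the fit. Only the step is missing.

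A reader might also infer that the tests give opposite answers. With an empty cell, a Wald test without a finite estimate is a visible failure to estimate, not a contrary verdict. The percentages depend on counting it as non-significant. The 22–70% range also needs differences of 60–70 points, which nothing in the documents predicts.

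The pilot table in Section 2.1 is weak support for empty cells. It covers six treated patients, of whom two or three were EEG+, and does not use the 50% threshold. Had every patient been a responder, there would be no comparison at all. Nor can a high TVR–PSI correlation be assumed: the text of Section 4.3 says power is normalised by volume, while the printed formula appears to multiply by it.

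Finally, the Statement of Compliance endorses guidance that moves away from significance thresholds. That lessens the weight of a deciding test but does not remove it, since Sections 8.1, 8.3 and 9 still rely on tests, p-values and a 0.05 error rate.

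**Conclusion.** The point holds as an inconsistency and a gap in specification. The responder rule has three possible readings; under the stated assumptions the joint and composite ones differ for about 2 to 8 of 20 patients. The step to the relative risk is unstated, and no test is given precedence.

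LR is significant without Wald in 6–17% of trials at 10 vs 10 and in 12–31% at 16 vs 4 or 17 vs 3 for moderate contrasts, rising to 22–70% for contrasts of 60–70 points. LR type I error ranges from 5.2% to 12.6% over the same splits at null rates of 50% and 70%. All rates and splits are assumptions.

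The Aim 4 hypothesis wording and the Section 9 calculation do not match the planned analysis. The plan should be changed, but these are secondary aims of a pilot and no primary conclusion is affected.

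**What to change.** Before outcome data are reviewed, the sponsor should:

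- State whether there is one composite rule (TVR >0.5 or PSI >0.5, as Section 4.3 is worded) or two analyses, one per measure, and use the same wording in Sections 3.3, 3.4, 4.3 and 8.3.
- Report the relative risk and risk difference with score or exact 95% intervals from the 2x2 table.
- Name one deciding exact test, Fisher or Boschloo, and its sidedness. For two-sided Boschloo, also state how the p-value is formed.
- Keep the logistic model as a sensitivity analysis.
- Reword the Aim 4 alternative as a proportion.
- Replace the Section 9 statement for Aim 4 with one for the chosen test at 20–22 analysable patients.

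The cost is wording, a few lines of code and some nominal power. In the eighteen scenarios tabulated, two-sided Fisher has about 7 to 23 points less power than LR. For 80 vs 40, for example, it is 25% against 48% at 10 vs 10, and 24% against 36% at 17 vs 3. Part of that loss reflects LR's inflated size. An exact 2x2 test does not adjust for covariates. If no non-responder improves, only the lower limit of the relative risk and the risk difference are informative. If all or no patients improve, or all are responders, no test helps.
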